8.3.2 Efficacy endpoints

- 8.3.2.1 Area under the C-peptide curve (AUC) over the first 2 hours of a 3-hour mixed meal tolerance test (MMTT). The AUC at 12-months and changes over time will be assessed.
- 8.3.2.2 Peak C-peptide levels over a 3-hour MMTT. The peak C-peptide level at 12-months and changes over time will be assessed.
- 8.3.2.3 Basal C-peptide levels at 12-months and changes over time will be assessed.
- 8.3.2.4 Daily insulin requirements
- 8.3.2.5 Change in HbA1C levels over time
- 8.3.2.6 Changes in auto-antibody levels over time

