- 1) CBC with different immune cell markers
- 2) Complete chemistry
- 3) EKG
- 4) Venous assessment done by an apheresis nurse. Patients without sufficient venous access will be deferred. Patients with acceptable venous access at the time of screening but who fail to collect peripherally

on the day of apheresis may have an apheresis catheter placed femorally by a surgeon for the purpose of the collection.

- 5) Autoantibody testing (see Table 3).
- 6) Infectious disease testing (HIV, HTLV, Hep B, cAB, Hep C ab.)

11.2 Visit 2

Women of childbearing potential will require a serum pregnancy test between day -7 and day -1.

The Mixed Meal Tolerance Test (MMTT): MMTT testing should be done in the morning while the subject is fasting. Subjects will be nothing by mouth (NPO) after midnight except water. Liquids that contain only simple sugars can be used to treat or prevent hypoglycemia during the night and morning prior to study. The target glucose level at the start of the test should be between 70 and 200 mg/dL for subjects with T1DM.

Insulin Application: Subjects with T1DM should take their usual dose of insulin on the evening before the test. Subjects on Lantus or Levemir should take their usual injection the evening before and/or on the morning of the test, as per their normal routine. Subjects on CSII should continue with their usual basal settings on night prior to test. Usual doses of rapid-acting insulin analog will be used until midnight the evening before the test. Small correction doses of rapid-acting insulin analog may also be used up to 4 hours before the test if needed to achieve a blood glucose level <150 mg/dL at the start of the study. Usual doses of NPH insulin and rapid-acting insulin analogs are not given on the morning of the test.

Blood Sampling: Blood will be obtained for measurement of plasma glucose, c-peptide and glucagon at -10, 0, 15, 30, 60, 90, 120, 150 and 180 minutes. A split-duplicate sample for quality control will also be collected. IV lines will be inserted in one arm for blood sampling.

Boost Dose: The mixed meal used will be Boost High Protein Gluten Free Drink with 20g of sugar per bottle. The MMTT should take 180 minutes to perform. The dose of Boost High Protein Gluten Free Drink with 20g of sugar per bottle, given at time 0 minutes. The dose should be consumed in no more than 5 minutes.

11.3 Visit 3

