12.1 Statistical Methods

This is a prospective, single-arm, open-label, single-center study to assess the safety, feasibility, and efficacy of SCE therapy for the treatment of patients with T1D. Ten patients meeting eligibility criteria will be enrolled for this study, with an effect size of 0.8 ng/mL at a 0.025 significance level and 80% power. All patients will be included in the safety analyses. The primary safety analysis will be performed in the safety population. The occurrences of treatment-related adverse events will be evaluated and presented as counts (percentages) and binomial 95% exact binomial confidence intervals (CI).

The feasibility of the SCE therapy will be assessed by analyzing the number of the patients unable to complete the therapy and the number of patients who are lost to follow-up prior to the 12-month visit. Both of these parameters will be analyzed as counts (percentages) and corresponding 95% CI as described in the safety analysis section above.

Statistical analyses of data will be performed by *t*-test using Power and Precision software (www.power-analysis.com). The paired *t* test will be used to study the significance between baseline and follow-ups. Using the fasting blood glucose levels and the plasma C-peptide, as well as their levels following OGTT or MMTT as the parameters, we want to detect the difference after the SCE therapy with an effect size of 0.8 ng/mL at 2.5% significance level, 80% power, and one side. According to our calculations, we will need 10 subjects in order to find this difference.

Area under the C-peptide curve will be calculated with C-peptide level measured at 0, 30, 60, 90, 120, 150 and 180 minutes of the MMTT using the trapezoid rule. The AUC for C-peptide over 120 minutes of the MMTT will be evaluated and summarized using descriptive stats mean (SD) or median (IQR), as appropriate. This calculation will be obtained for each of the time points, baseline, 3, 6, 9, 12, and 24 months and longitudinal analysis will be performed to evaluate the changes over time. This analysis of changes over the time points will be achieved using mixed effect models for repeated measures (MMRM) implemented using PROC MIXED in SAS version 9.4. As this is a secondary analysis no adjustment for multiple test will be employed for this analysis.

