Mean AUC for C-peptide over 3 hour MMTT, which is defined as the AUC divided by the duration of the test i.e., 180 minutes, will be calculated at baseline, and all subsequent post-baseline points, and changes over time will be analyzed using MMRM method as defined in the AUC for C-peptide subsection above.

HbA1C levels assessed at baseline, 3, 6, 9, 12, and 24 months will be summarized using descriptive statistics at each time point. To evaluate changes in HbA1C levels assessed at baseline and post-baseline time points, the MMRM analysis defined in AUC for C-peptide will be performed.

All study data will be entered into a Microsoft Office Excel 2013 (Microsoft Corporation, Redmond, WA) and imported into SAS 9.4. The database will be validated in SAS to ensure any out of range values are queried for all multiple source until all data issues are resolved. Any $p < 0.05$ will be considered statistically significant. All data analysis will be performed using SAS version 9.4 (SAS Institute Inc. Cary, NC).

Stopping rule: If a grade 3 adverse event, as per the Common Terminology Criteria for Adverse Events (CTCAE) Version 4.0, related to the study procedure occurs in 2 patients, the study will be terminated.

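### The C-peptide AUC formula leaves out the 15-minute MMTT sample that the protocol already draws; using it is a small but free gain in precision

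*Combined protocol and SAP*

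**What the plan says.** Section 11.2 (Visit 2) sets the sampling: "Blood will be obtained for measurement of plasma glucose, c-peptide and glucagon at -10, 0, 15, 30, 60, 90, 120, 150 and 180 minutes". The meal is "given at time 0 minutes", so the −10 and 0 minute samples are both pre-meal values.

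Section 12.1 sets the calculation, by the trapezoid rule: "Area under the C-peptide curve will be calculated with C-peptide level measured at 0, 30, 60, 90, 120, 150 and 180 minutes". On the window, that section says: "The AUC for C-peptide over 120 minutes of the MMTT will be evaluated". This matches the first efficacy endpoint in 8.3.2, which the study summary lists among the secondary endpoints. Section 12.1 adds a second summary: "Mean AUC for C-peptide over 3 hour MMTT, which is defined as the AUC divided by the duration of the test", that duration being 180 minutes.

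The two lists differ at −10 and 15 minutes. The plan does not explain the difference and gives no rule for using the −10 value. Section 12.2 calls change in C-peptide secretion the primary efficacy endpoint without naming the measure. The AUC is treated here as 8.3.2 and 12.1 treat it, as a secondary measure.

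**The concern.** The 15-minute sample is drawn and measured for C-peptide but does not enter the AUC. Without it, the trapezoid rule draws a straight line from 0 to 30 minutes, across the start of the post-meal rise. The single 0-minute value then carries 15 minutes of weight and the 30-minute value carries 30. With it, those weights fall to 7.5 and 22.5, and the early curve is followed more closely.

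With 10 patients, precision that costs nothing is worth taking. What is at stake is a little extra measurement noise and a slightly larger trapezoid error in each patient's AUC.

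**Working it through.** **Figures in the plan.** The documents give no SD, assay error or precision target for the AUC, so there is no stated figure to reproduce. The sample size of 10 does not enter this check.

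**Inputs from the documents.** Sampling times (11.2), times in the formula and the trapezoid rule (12.1), and the 120-minute and 180-minute windows (8.3.2 and 12.1). Section 11.2 gives the sampling times under Visit 2 only; I assume that follow-up tests use the same times.

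**Step 1: measurement error.** With trapezoid weights wᵢ and independent errors of equal SD σ, Var(AUC) = σ² × Σwᵢ².

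- Planned grid, 0–120: weights 15, 30, 30, 30, 15. Σw² = 225 + 900 + 900 + 900 + 225 = 3150.
- With 15 minutes: weights 7.5, 15, 22.5, 30, 30, 15. Σw² = 56.25 + 225 + 506.25 + 900 + 900 + 225 = 2812.5.
- With 15 minutes, and time 0 taken as the mean of −10 and 0: the first term halves to 28.125. Σw² = 2784.4.

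| Change to the grid, AUC(0–120) | Variance ratio | Variance falls | SD falls |
|---|---|---|---|
| Add 15 min | 2812.5/3150 = 0.893 | 10.7% | 5.5% |
| Add 15 min and average −10 with 0 | 2784.4/3150 = 0.884 | 11.6% | 6.0% |
| Average −10 with 0 only | 3037.5/3150 = 0.964 | 3.6% | 1.8% |

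For AUC(0–180), Σw² goes from 4950 to 4612.5 with 15 minutes and to 4584.4 with both changes. The SD falls by 3.5% and 3.8%.

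**Step 2: effect on the quantity analysed.** Let τ be the SD between patients of the true change in mean C-peptide over 0–120. The SD of the observed change between two visits is √(τ² + 2σ²Σw²/120²). Neither σ nor τ is in the documents, so both are assumed, in ng/mL. The percentage fall in this SD with both changes made is:

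| σ per sample | τ = 0.2 | τ = 0.4 | τ = 0.8 |
|---|---|---|---|
| 0.05 | 0.15 | 0.04 | 0.01 |
| 0.1 | 0.57 | 0.15 | 0.04 |
| 0.2 | 1.78 | 0.57 | 0.15 |
| 0.3 | 2.92 | 1.15 | 0.34 |

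Worst case (σ = 0.3, τ = 0.2): √(0.04 + 0.18 × 3150/14400) = 0.2817 against √(0.04 + 0.18 × 2784.4/14400) = 0.2735, a fall of 2.9%. The 15-minute sample alone gives √(0.04 + 0.18 × 2812.5/14400) = 0.2741, a fall of 2.7%.

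**Step 3: trapezoid error.** On assumed smooth curves f(t) = b + a(t/p)exp(1 − t/p), with a = 2b and the peak at p minutes, the AUC(0–120) is underestimated as follows.

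| Peak time p | Without 15 min | With 15 min |
|---|---|---|
| 60 | 2.43% | 1.31% |
| 90 | 1.59% | 1.02% |
| 120 | 1.16% | 0.80% |

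If the curve keeps its shape between visits, this acts as a small common scale factor and matters little for change. If the shape changes, it does not cancel exactly.

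**The case against.** The strongest reply is that nothing here is wrong. Section 12.1 fixes one definite, evenly spaced grid before any data are seen, and the trapezoid rule on that grid is valid. The 15-minute draw also serves glucose and glucagon. The AUC is a secondary analysis with no precision target to miss. All of this stands, and it is why the point is a suggestion. It does not supply a reason for leaving out a C-peptide value that is measured anyway and lies inside the window.

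A reader might infer more from the mismatch than it supports:

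- *That the formula also wrongly omits the −10 sample.* That sample precedes the meal and lies outside 0–120, so it cannot be a trapezoid node of this AUC. It can enter only by averaging with time 0, which no section provides for. On top of the 15-minute sample, averaging moves the SD reduction only from 5.5% to 6.0%.
- *That 11.6% is the gain in the efficacy analysis.* It is the fall in measurement-error variance alone. Between-patient variation in change dilutes it to the small figures in Step 2.
- *That an earlier post-meal rise at follow-up would be seriously misread.* In two constructed cases with the same peak and an earlier rise, the AUC change was off by 1.6 to 1.9 ng/mL × min without the 15-minute sample and 0.2 to 0.5 with it. Divided by 120, the larger errors are 0.013 to 0.016 ng/mL of mean C-peptide, at most about 2% of the 0.8 ng/mL in 12.1 ("effect size of 0.8 ng/mL at 2.5% significance level, 80% power, and one side"). The documents contain no MMTT curve to support such cases, so they are only illustrative.
- *That the mean of −10 and 0 should become the basal C-peptide value.* Basal C-peptide is a separate endpoint (8.3.2.3), and Table 3 has its own fasting C-peptide row. The documents do not equate that value with the MMTT time-0 value, so such a rule could create a new ambiguity.

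**Conclusion.** The point holds as a minor, free improvement. The protocol draws a 15-minute C-peptide sample within the AUC window and the formula does not use it. Using it cuts the measurement-error SD of AUC(0–120) by 5.5%, assuming independent errors of equal variance and the same sampling at every visit. On assumed smooth curves it also reduces the trapezoid underestimate, from 1.2–2.4% to 0.8–1.3%. For the SD of the change from baseline the gain is about 0 to 3% over the assumed SDs. It is unlikely to change any conclusion in 10 patients. The planned formula is neither invalid nor biased in a way that would undermine the endpoint.

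**What to change.** In 12.1, replace the list of times with a rule such as: *AUC by the trapezoid rule from the MMTT C-peptide values at 0, 15 and 30 minutes and every 30 minutes thereafter to 180, with the same times at every visit; the 120-minute AUC uses the values up to 120 minutes.* Apply the same grid to the 180-minute mean AUC.

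Optionally, add that the time-0 node is the mean of the −10 and 0 minute values, and say that this applies to the AUC only and leaves the basal C-peptide endpoint in 8.3.2.3 as it is.

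The cost is one or two sentences, best added before any MMTT data are analysed. It needs no further sample, visit or patient and does not touch clinical management.

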12.2 Subject Population(s) for Analysis

All subjects who received treatment will be included in the safety analyses. The primary efficacy end point will be the change in C-peptide secretion between baseline and follow-up.

13 Safety and Adverse Events

13.1 Definitions

13.1.1 Unanticipated Problems Involving Risk to Subjects or Others

Any incident, experience, or outcome that meets all of the following criteria:

- Unexpected in nature, severity, or frequency (i.e. not described in study-related documents such as the IRB-approved protocol or consent form, the investigators brochure, etc)
- Related or possibly related to participation in the research (i.e. possibly related means there is a reasonable possibility that the incident experience, or outcome may have been caused by the procedures involved in the research,
- Apheresis-related side effects such as citrate toxicity (symptomatic hypocalcemia), hypotension, vasovagal reaction, and access site thrombophlebitis. If central venous catheter (CVC) is used, additional adverse events include bleeding at the cvc site, deep-vein thrombosis (DVT), thrombophlebitis, and central line infections.
- Serious (as defined below) “Serious” is different than “severe” as reported in the CTC criteria that applies a grade to the AE.

13.1.2 Adverse Event

An **adverse event** (AE) is any symptom, sign, illness or experience that develops or worsens in severity during the course of the study. Concurrent illnesses or injuries should be regarded as adverse events. Abnormal results of diagnostic procedures are considered to be adverse events if the abnormality:

- results in study withdrawal
- is associated with a serious adverse event
- is associated with clinical signs or symptoms
- leads to additional treatment or to further diagnostic tests
- is considered by the investigator to be of clinical significance

13.1.4 Adverse Event Reporting Period

The study period during which adverse events must be reported is normally defined as the period from the initiation of any study procedures to the end of the study treatment follow-up.

For this study, the study treatment follow-up is defined as 30 days following the administration of study treatment. Serious adverse events should be reported to the local IRB and FDA within 7-10 days from the time of the event. Minor events can be reported in an annual report

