8.2 Primary Study Endpoint

The primary study endpoint will be the occurrence of treatment-related adverse effects. Adverse events that occur during therapy (especially those that necessitate temporary or permanent discontinuation of therapy) and over the 12-month follow-up period will be assessed.

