13.2 Recording of Adverse Events

Based on our current clinical data in 200 subjects including Chinese and Caucasian patients, we did not see any significant adverse events during the treatment with SCE therapy, and follow-up studies after treatment for 4 years. No participants experienced any significant adverse events during the course of treatment. Most patients experienced mild discomfort during venipuncture and some soreness of the arm during aphaeresis, but discomfort and soreness resolved quickly following the conclusion of the procedure. No tumor formation and other safety concerns in all subjects after receiving SCE for 4 years.

At each contact with the subject, the investigator must seek information on adverse events by specific questioning and, as appropriate, by examination. Information on all adverse events should be recorded immediately in the source document, and also in the appropriate adverse event module of the case report form (CRF). All clearly related signs, symptoms, and abnormal diagnostic procedures results should be recorded in the source document, though should be grouped under one diagnosis.

All adverse events occurring during the study period must be recorded. The clinical course of each event should be followed until resolution, stabilization, or until it has been determined that the study treatment or participation is not the cause. Serious adverse events that are still ongoing at the end of the study period must be followed up to determine the final outcome. Any serious adverse event that occurs after the study period and is considered to be possibly related to the study treatment or study participation should be recorded and reported immediately.

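### The primary safety endpoint runs for 12 months, but the adverse-event reporting period ends at 30 days, leaving no consistent duty to report later non-serious related events

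*Combined protocol and SAP*

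**What the plan says.** All references are to the combined protocol and SAP.

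- **8.2 (primary endpoint).** The endpoint is treatment-related adverse events, with no restriction to serious ones. Events during therapy "and over the 12-month follow-up period will be assessed".
- **13.1.4 (reporting period).** The general rule begins "The study period during which adverse events must be reported is normally defined as the period from the initiation of any study procedures" and ends with study treatment follow-up. The study-specific definition is: "For this study, the study treatment follow-up is defined as 30 days following the administration of study treatment".
- **13.2 (recording), towards a long window.** "At each contact with the subject, the investigator must seek information on adverse events by specific questioning". "Information on all adverse events should be recorded immediately in the source document", and also in the CRF. Neither instruction has an end date.
- **13.2, towards a bounded window.** "All adverse events occurring during the study period must be recorded". For what comes later, the section names only this class: "Any serious adverse event that occurs after the study period and is considered to be possibly related to the study treatment" or participation.
- **13.1.2 and 13.1.6.** An adverse event is one that "develops or worsens in severity during the course of the study", and new clinically significant findings at the end of the study are to be recorded. Both suggest the longer window.
- **12.1 (analysis).** Treatment-related events are summarised as counts and percentages with exact binomial 95% intervals. No time window is given.
- **12.1 and 13.4 (stopping rule).** Two patients with a procedure-related grade 3 event end the study. No time limit is given.
- **9.4.2 and 13.1.7.** These set 12 weeks of toxicity data after withdrawal, and a 6-month notification window after participation ends.

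**The concern.** The endpoint definition and the rule that supplies its data use different periods. Site staff who work from 13.1.4 may stop submitting non-serious events after day 30. Staff who work from the first part of 13.2 will go on asking and recording. The same event could be handled either way, and nothing in the plan says which section prevails.

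The resulting error has one direction. Missed events can only lower the primary count, so the point estimate and its exact interval would look safer than a 12-month endpoint supports. In a single-arm safety pilot there is no control group in which a similar loss might offset it.

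The stopping rule draws on the same data. Section 13.1.1 separates seriousness from CTC severity grade, so a related grade 3 event need not be serious. If it is not serious and occurs after day 30, the post-period clause of 13.2 does not cover it.

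**Working it through.** The plan gives no figure of its own to reproduce here. The check compares the windows, then asks what a missed patient would do to the primary result.

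**1. One event traced through the sections.** Take a non-serious, treatment-related event at Month 6 in a subject still in follow-up.

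| Section | Treatment of the event |
|---|---|
| 8.2 | Counts towards the primary endpoint |
| 13.1.4 | Outside the period in which reporting is required |
| 13.2, questioning and source/CRF instructions | To be sought and recorded |
| 13.2, mandatory sentence | Depends on what *study period* means; 13.1.4 gives the only definition containing the term |
| 13.2, post-period clause | Not covered, because not serious |
| 13.1.2, 13.1.6 | Suggest it is captured |
| 9.4.2, 13.1.7 | Do not apply; they concern subjects who have withdrawn or ended participation |
| 12.1 | Silent on the window |

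**2. Share of the endpoint window covered.** 30/365 = 0.082, or 8.2%. The remaining 365 − 30 = 335 days (91.8%) lie outside. This is calendar time, not risk.

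**3. Scheduled contacts (11.5 to 11.11).** After infusion there are Day +1 to +2, Day +7, and Months 1, 3, 6, 9 and 12, making 7 contacts through Month 12. Months 3, 6, 9 and 12 fall wholly after day 30: 4 of 7. Month 1 ± 5 days is about days 25 to 35 (taking a 30-day month), so it straddles the cut-off.

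**4. Effect on the primary estimate.** Inputs: n = 10 and exact binomial 95% intervals, both from 12.1. The Clopper-Pearson limits are the 0.025 quantile of Beta(x, n − x + 1) and the 0.975 quantile of Beta(x + 1, n − x), with lower limit 0 when x = 0.

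| Patients with an event | Rate | Exact 95% CI |
|---|---|---|
| 0/10 | 0% | 0% to 30.8% |
| 1/10 | 10% | 0.3% to 44.5% |
| 2/10 | 20% | 2.5% to 55.6% |

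For 0/10 the upper limit is 1 − 0.025^(1/10) = 0.308. Each patient whose only related event is missed lowers the rate by 1/10 = 10 percentage points and moves the result up one row of the table.

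**5. Effect on the stopping rule.** The threshold is 2 patients. If one of two affected patients is missed, the count is 1 and the rule is not met.

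**6. Can the loss be sized?** No. The documents give no event rate or timing. As an assumption only, take a constant hazard, so that 30-day risk = 1 − (1 − p)^(30/365) for 12-month risk p. For p = 10%, 30% and 50% this gives 0.9%, 2.9% and 5.5%, so about 9% to 11% of the 12-month risk falls in the first 30 days. If events instead cluster around apheresis and infusion, most fall inside 30 days and the loss is small. How many late events staff would actually fail to record is also unknown.

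**The case against.** The best defence is that 13.1.4 concerns reporting, while the endpoint is built from recorded data. The sentences after the 30-day definition deal with reports to the IRB and FDA and with annual reports. Recording belongs to 13.2, which sends events to source and CRF without a cut-off. On this reading the Month 6 event is recorded and counted even though it falls outside the external reporting window.

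Other text supports that intention:

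- Section 14.1 uses *study period* for a subject's full schedule, so 13.2 may also mean the whole study.
- The adverse-event monitoring row of Table 3 may be marked continuous. The table is broken in the available text, so this cannot be confirmed.
- Section 13.1.7 can be read to include completers and covers related events of any seriousness. It would be odd to want those after participation ends but not between day 30 and Month 12.

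It can be added that this is a single infusion, that the reactions the protocol names are mainly procedural, and that the primary analysis is descriptive.

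Much of this stands. Later capture was probably intended and is not excluded, and any actual loss may be small. But the plan never states the distinction between recording and reporting, and 13.2 ties its own recording duty to the term used in 13.1.4. A continuous entry in Table 3 would add to the conflict with 13.1.4, not remove it. Section 13.1.7 takes effect only once participation has ended, so it does not reach a subject still in follow-up at Month 6. A descriptive primary analysis still needs one defined collection window.

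**Conclusion.** The concern holds. The plan assesses its primary endpoint over 12 months and sets a study-specific 30-day end to adverse-event reporting, and no section reconciles the two. The gap is limited to non-serious related events after day 30, including grade 3 events that are not serious; serious, possibly related events after the period do have a duty under 13.2. It is a lack of a consistent duty, not the absence of any duty.

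The mismatch spans 91.8% of the endpoint window and 4 of 7 scheduled contacts. At n = 10, one missed patient is enough to change the headline safety result or leave the stopping rule unmet. Those examples assume that a late event is in fact missed. No bias estimate is claimed. The point must be fixed because it governs what enters the primary endpoint, and events not collected at the time may not be recoverable later.

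**What to change.** 1. Rewrite 13.1.4 so that the adverse-event recording and reporting period runs from the first study procedure through at least the Month 12 visit, matching 8.2. Extension to Month 24 is optional.
2. Make *study period* in 13.2 refer explicitly to that window.
3. State the window in the primary safety analysis in 12.1.
4. Reconcile the 12-week window in 9.4.2 and the 6-month window in 13.1.7 with it, as far as consent allows for withdrawn subjects.
5. If a 30-day acute summary is wanted, define it as a separate, named analysis.

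The cost is protocol wording and a little extra data entry at the Month 3, 6, 9 and 12 visits already scheduled. No new visits are needed.
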